4.7.3 Additional safety assessments

By-visit summaries of laboratory variables and vital signs will be presented by age cohort and overall for the Safety Analysis Set. Shifts and potentially clinically significant laboratory abnormality (PCSA) summaries will be presented by age cohort and overall for the Safety Analysis Set.

4.7.3.1 Laboratory variables

Blood samples for clinical laboratories will be taken at all scheduled visits. Clinical laboratory values will be analyzed after conversion into standard international units; international units will be used in all listings and tables. Data collected at local laboratories will be only included in the PCSA analysis and listing, and shift summary.

The laboratory parameters will be classified as follows:

- Hematology
 - Red blood cell (RBC) count
 - White blood cell (WBC) count and differential
 - Hemoglobin (Hgb)
 - Hematocrit (HCT)
 - Platelet count
- Clinical chemistry
 - Alanine aminotransferase (ALT)
 - Aspartate aminotransferase (AST)
 - Alkaline phosphatase (ALP)
 - Gamma glutamyl transferase (GGT)
 - Bilirubin
 - Blood Urea Nitrogen (BUN)
 - Creatinine
 - Glucose
 - Total protein
 - Potassium
 - Sodium
 - Chloride
- von Willebrand Comprehensive panel
 - VWF ristocetin cofactor activity
 - VWF antigen

All laboratory evaluations will be summarized for the Safety Analysis Set. Laboratory evaluations taken during major surgical/rehabilitation periods will not be included in the summaries. In the event of retests or repeat assessments at the same time point, the last non-missing evaluable measurement will be used for the purpose of analysis. Laboratory values of the form "<x" (ie, below the lower limit of quantification [LLOQ]) or ">x" (ie, above the upper limit of quantification [ULOQ]) will be imputed as "x" in the calculation of summary statistics but displayed as "<x" or ">x" in the listings.

Statistical Analysis Plan BIVV001-EFC16295 23-Aug-2021 Version number: 1

Change from baseline

The summary statistics (including number, mean, median, standard deviation, minimum and maximum) of all laboratory variables (central laboratory values and changes from baseline) will be calculated for each visit by age cohort and overall.

Shifts

Each participant's laboratory values will be classified according to whether the test result is "low" (below the lower limit of normal [LLN]), "normal" (within the normal range), or "high" (above the upper limit of normal [ULN]). Shift tables will be constructed based on both the minimum and maximum post baseline values for each participant. Data collected from unscheduled visits will be included in the determination of the per participant minimum and maximum values.

A separate table will be provided which summarizes the results of the shift tables in which the number and percentage of participants with a shift to low (from normal, high, or unknown) and the number of participants with a shift to high (from normal, low, or unknown) will be tabulated; percentages will be based on the number of participants at risk. The number at risk for a shift to low (high) is the number of participants whose baseline value was not low (high), including unknown, who had at least one post-baseline value. Only directions of change indicating a clinical concern will be included in this table summarizing the shifts. The direction of concern is provided in Table 5.

Laboratory test	Direction	Laboratory test	Direction
	Chemistry	Hematology	
Liver		White blood cells	Low and High
ALP	High	Lymphocytes	Low and High
ALT/SGPT	High	Neutrophils	Low and High
AST/SGOT	High	Monocytes	Low and High
Total bilirubin	High	Eosinophils	Low and High
GGT	High	Basophils	Low and High
Renal		Red blood cells	Low and High
Blood urea nitrogen	High	Hemoglobin	Low and High
Creatinine	High	Hematocrit	Low and High
Electrolytes		Platelets	Low and High
Sodium	Low and High		
Potassium	Low and High	C	pagulation
Chloride	Low and High	VWF antigen	Low
Other		VWF:RCo activity	Low
Glucose	Low and High		
Total protein	Low and High		

Table 5 - Direction of	f change indicatin	a clinical concern	for laboratory tests
	onungo maioum	g omnour oonoorn	101 1000101019 10010

Potentially Clinically Significant Laboratory Abnormalities

Abnormal laboratory values will also be evaluated by determining the number and percentage of participants with at least one PCSA over the course of the study that also represents a worsening from baseline. The PCSA values are defined as abnormal values considered medically important by the Sponsor according to predefined criteria/thresholds based on literature review and defined by the Sponsor for clinical laboratory tests and vital signs (APPENDIX 4 [Section 5.4]).

Participants who have a post baseline laboratory value that meets the criteria for being potentially clinically significant but do not have a baseline value will be included in the numerator for determining the percentage of participants with an abnormality. Percentages will be based on the number of participants with at least one post baseline value for the given laboratory test. Data collected from unscheduled visits will be included in this analysis.

4.7.3.2 Vital signs and physical examination

Vital signs will be taken at Baseline, Weeks 4, 26 and 52. Vital signs include temperature, pulse rate, respiratory rate and blood pressure. All vital sign evaluations will be summarized for the Safety Analysis Set. Data from unscheduled visits and vital sign measurements taken during major surgical/rehabilitation periods will not be included in any summary but will be included in the listings and flagged.

Change from baseline

The summary statistics (including number, mean, median, standard deviation, minimum and maximum) of all vital sign variables (and changes from baseline) will be calculated for each visit by age cohort and overall for the Safety Analysis Set. Evaluations taken during major surgical/rehabilitation periods will not be included in any summary.

Potentially Clinically Significant Vital Sign Abnormalities (PCSA)

Frequencies and percentages of participants with potentially clinically significant abnormalities will be summarized by age cohort and overall. Percentages will be based on the number of participants with a baseline and at least one post baseline value. Vital sign abnormality thresholds are defined in APPENDIX 4 (Section 5.4).

All physical examination findings are presented in a by-participant data listing.

4.8 OTHER ANALYSES

4.8.1 Pharmacokinetic analyses

All PK analyses will be performed based on the PK analysis set (PKAS).

If a repeat PK profile is required due to bleeding (or other reason) during the PK evaluations, then only the repeat profile will be used for the summary of the FVIII activity levels and in the analysis of PK summary parameters. Data from incomplete profiles will be included in data listings.

Actual sampling times, doses, and injection durations will be used for PK analysis. Nominal sampling times and doses will be used for the creation of tables, figures and listings.

FVIII activity values for each timepoint will be corrected for baseline activity at Day 1 using the residual decay function. The detailed methodology used to correct baseline activity will be provided either in the clinical study report or PK report. PK parameters will be computed using baseline corrected FVIII activity values.

PK parameters will be estimated using FVIII activity values measured by aPTT-baseline onestage clotting assay, and values measured by chromogenic coagulation assay.

For participants undergo PK sampling at Day 1, for each participant using noncompartmental methods the following pharmacokinetic parameters will be included but not limited to: maximum FVIII activity (C_{max}), terminal half-life (t1/2), total clearance (CL), clearance at steady state (CL_{ss}), volume of distribution at steady state (Vss), area under the plasma FVIII activity-time curve from time zero to end of dosing period (AUC_{0-tau}), dose-normalized area under the activity-time curve (DNAUC), mean residence time (MRT), incremental recovery (IR), trough activity (C_{trough}) and time to 1% FVIII activity level.

The detailed methodology for computing PK parameters using noncompartmental method will be described in the CSR or PK report. The detailed methodology for computing PK parameters using population PK method will be described in the population PK report.

The population PK analysis will be presented separately from the main CSR. Population PK analysis will be described fully in the population PK analysis plan and will be finalized before database lock.

For the PKAS the following analyses will be performed:

- For each assay type, a summary table of FVIII activity levels will be provided for BIVV001 at scheduled PK visits and time points for the PK subgroup (Baseline BIVV001). Summary descriptive statistics will include the number of non-missing values, mean, geometric mean, standard deviation, percent coefficient of variation, minimum, and maximum. In these summaries, values below the LLOQ will be imputed as zero.
- For each assay type, individual PK parameters will be listed for each participant and summarized descriptively for the PK subgroup (Baseline BIVV001). Any FVIII assessments flagged by the PK scientist as being implausible and excluded from computation of PK parameters will be excluded from summaries but included in listings. The listings will indicate which values, if any, were excluded from summaries. A separate listing of excluded values, together with the reason for exclusion will be provided.

In addition, for each assay type, the peak and trough concentrations will be summarized by visit for the FAS. The incremental recovery will also be summarized by visit for the FAS. Summary descriptive statistics will include the number of non-missing values, mean, geometric mean, median, Q1, Q3, standard deviation, percent coefficient of variation, minimum, and maximum. In these summaries, values below the LLOQ will be imputed as zero.

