- cc* Patient-Reported Outcomes Measurement Information System (PROMIS) Assessments to include Pain Intensity, Pain Interference (PROMIS Pediatric-SF Pain Interference <18 years old), and Physical Function (PROMIS Pediatric-SF Physical Activity <18 years old). The PROMIS instruments will be administered to participants \geq 8 years old and to parent proxy for participants aged 5-12 years.
- dd* The Haemo-QoL children version will be administered to participants \geq 4 years old and the parent will be administered a parent proxy version (\geq 4 years old).
- ee* The EQ-5D-Y children version will be administered to participants \geq 8 years old and the parent version will be administered to parent proxy (for participants 4-7 years old).

Table 2 - PK sampling schedule of activities (PK subgroup)

Assessments ^a	Pre-dose	Post-dose ^c				
	Day 1 Week 1 ^b	Day 1 Week 1		Day 2	Day 4	Day 8 ^d
		15 minutes (±3) minutes	3 hours (±15 minutes)	24 hours (±2 hours)	72 hours (±5 hours)	168 hours (±5 hours)
FVIII activity (measured by one-stage clotting aPTT and two-stage chromogenic assays) ^e	X	X	X	X	X	X

Abbreviations: aPTT = activated partial thromboplastin assay; FVIII = Factor VIII; PK = pharmacokinetics.

NOTE: Initial dosing of BIVV001 is in the clinic on Day 1 Week 1.

- a For a subset of participants who are in the PK subgroup (n=24). Baseline PK sampling can be conducted optionally after full enrollment of the PK subgroup in other participants at the discretion of investigator through central laboratory.
- b Washout of at least 96 hours (4 days) for 6 to <12 years participants and at least 72 hours (3 days) for <6 years participants prior to sample collection is required. Pre-dose samples are collected within 30 minutes prior to dosing. The washout period may be modified at the discretion of the Investigator based on individual PK data and clinical phenotype in consultation with medical monitor.
- c All sampling times are relative to the start of injection.
- d Before injection of the next dose of BIVV001. Study drug can be taken after assessments on Day 8.
- e Details regarding sample handling and volume in relation to body weight are provided in the Central Laboratory Manual.

Table 3 - Surgical schedule of activities

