1 INTRODUCTION

1.1 STUDY DESIGN

This is a multinational, multicenter, open-label Phase 3 study of the safety, efficacy and pharmacokinetics (PK) of BIVV001 in previously treated patients (PTPs) <12 years of age with severe hemophilia A (defined as <1 IU/dL [<1%] endogenous FVIII).

The study is comprised of <6 years and 6 to <12 years age cohorts, where participants will receive BIVV001 at a dose of 50 IU/kg IV QW for 52 weeks. Approximately 65 participants will be enrolled to achieve at least 50 participants (25 participants <6 years of age and 25 participants 6 to <12 years of age) completing approximately 52 weeks of treatment to obtain at least 50 exposure days (EDs). Enrollment in a planned open-label extension study will be offered to participants after completion of this study.

[figure not shown]

Figure 1 - Study schema

Abbreviations: EOS = end of study; FU = follow-up; IV = intravenous; PTP = previously treated patient.

a The safety follow-up call or visit will occur 2 to 3 weeks after the last dose of BIVV001, unless the participant enrolls in the open-label extension study.

All enrolled participants will come in to scheduled visits at Baseline (Day 1), Week 4, Week 13, Week 26, Week 39 and Week 52.

Following a washout period (at least 3 to 4 days, depending on age), the first 24 participants from the 2 age cohorts (at least 12 participants <6 years of age and at least 12 participants 6 to <12 years of age) will undergo PK sampling after their first dose of BIVV001 (Baseline).

In addition, participants who undergo major surgery during the study will be included in the surgery subset to assess control and prevention of bleeding during use of BIVV001 in the surgical setting.

Participants will be offered enrollment in an open-label extension study after completion of this study based on eligibility criteria.

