2 SAMPLE SIZE DETERMINATION

The determination of the number of participants is based on clinical rather than statistical considerations. Taking into consideration the guideline from Committee for Medicinal Products for Human Use (EMEA/CHMP/BPWP/144533/2009 rev.2), approximately 65 PTPs will be enrolled to obtain at least 50 participants with at least 50 EDs at the end of the study. All eligible participants completing or remaining at the end of study will be offered participation in the planned extension trial.

At least 12 participants in each age cohort need to have completed adequate blood sample collection to assess key PK parameters.

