4 STATISTICAL ANALYSES

All summaries and statistical analyses will be generated using SAS Version 9.0 or higher.

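### SAP 4.8.1 sets values below the quantification limit to zero in two tables that report a geometric mean; any cell with such a value then gives 0, or a mean computed without its lowest values

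*SAP*

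**What the plan says.** SAP 4.8.1 (Pharmacokinetic analyses) describes two sets of FVIII activity summaries for each assay.

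- **PK subgroup, activity by scheduled time point.** "Summary descriptive statistics will include the number of non-missing values, mean, geometric mean, standard deviation, percent coefficient of variation, minimum, and maximum".
- **FAS, peak and trough (and incremental recovery) by visit.** The statistics are the number of non-missing values and "mean, geometric mean, median, Q1, Q3, standard deviation, percent coefficient of variation, minimum, and maximum".

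Each description ends with the same rule: "In these summaries, values below the LLOQ will be imputed as zero". Neither document gives a separate rule for the geometric mean, and no count of values below the LLOQ (BLQ values) is planned. SAP section 4 adds only that "All summaries and statistical analyses will be generated using SAS Version 9.0 or higher", which does not settle how a zero enters a geometric mean.

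The SAP handles BLQ results differently elsewhere. Under 4.7.3.1, a safety laboratory result below the LLOQ is set to the limit itself.

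**The concern.** The geometric mean is the n-th root of a product, or equivalently the exponential of the mean log. A zero breaks both forms. The product becomes 0 whatever the other values are, and the log of zero is undefined. The stated rule therefore leads to one of two outcomes, and two programmers following the SAP could report different numbers.

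If the zero is kept, the cell shows 0 and carries no information. If log(0) is treated as missing, the lowest observations leave the calculation and the geometric mean is too high. The imputed zeros still count as non-missing, so n would not show that fewer values were used.

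**Working it through.** **Inputs.** The documents give no LLOQ and no BLQ frequency, so there is no planned figure to reproduce. From the documents: the zero rule and the lists of statistics (SAP 4.8.1); at least 12 PK participants per cohort (SAP section 2: "At least 12 participants in each age cohort need to have completed adequate blood sample collection to assess key PK parameters"); a target of 25 completers per cohort (SAP 1.1). Everything marked as assumed below is mine to vary.

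**Step 1. The rule itself.** GM = (x1 × x2 × … × xn)^(1/n) = exp(mean of ln x). One x = 0 gives GM = 0 by the first form and an undefined term by the second. This step needs no assumption.

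**Step 2. Where BLQ values are likely.** SAP 1.1 requires endogenous FVIII below 1 IU/dL. Protocol Table 2 has a pre-dose time point: "Pre-dose samples are collected within 30 minutes prior to dosing". It follows a washout of at least 72 hours under 6 years; for the older cohort the text is "Washout of at least 96 hours (4 days) for 6 to <12 years participants". In Protocol 2.2.3.1 the conventional FVIII comparator averaged 0.7% at 72 hours after 25 IU/kg in adults, and 2.3% after 65 IU/kg. BLQ values at Day 1 pre-dose are therefore realistic, though not certain in every child. That sample reaches both tables: the PK subgroup through the pre-dose time point, and the other participants through the Day 1 trough (Protocol 8.5).

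**Step 3. How often a cell is hit.** With an assumed BLQ probability p per independent sample, P(at least one in 12) = 1 − (1 − p)^12. This gives 11% for p = 1%, 46% for 5%, 72% for 10% and about 100% for 50%.

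**Step 4. Pre-dose example (assumed).** Take 12 participants, 9 BLQ, the others at 1.2%, 1.8% and 2.5%. Zeros kept: GM = 0. Zeros dropped: (1.2 × 1.8 × 2.5)^(1/3) = 5.4^(1/3) = 1.75, from 3 values under a printed n of 12. The arithmetic mean with zeros is 5.5/12 = 0.46.

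**Step 5. Trough example (assumed).** Take 25 troughs, k of them BLQ, and detectable values with GM 6%. If BLQ values are set to v, GM = exp(((25 − k) ln 6 + k ln v)/25). Dropping them gives 6.0, so the overstatement is (6/v)^(k/25) − 1.

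| k | v (%) | How v arises | GM with v | Overstatement if dropped |
|---|---|---|---|---|
| 1 | 1 | LLOQ 1%, set to LLOQ | 5.59 | 7% |
| 1 | 0.5 | LLOQ 1% halved, or LLOQ 0.5% | 5.43 | 10% |
| 1 | 0.25 | LLOQ 0.5% halved | 5.28 | 14% |
| 2 | 1 | LLOQ 1%, set to LLOQ | 5.20 | 15% |
| 2 | 0.5 | LLOQ 1% halved, or LLOQ 0.5% | 4.92 | 22% |
| 2 | 0.25 | LLOQ 0.5% halved | 4.65 | 29% |

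In every row, keeping the zeros gives 0. The overstatement is relative to the substituted result, which is itself a convention.

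**The case against.** The strongest reply is that the likely trigger and the important quantity are different samples. The Day 1 pre-dose sample is taken before any BIVV001, so a geometric mean of 0 there says nothing about weekly dosing. For 168-hour troughs, the only readable figures are adult means at 50 IU/kg of 9.16% (one-stage) and 6.51% (chromogenic), in Protocol 2.2.3.2. If troughs were lognormal with median 6% and a CV of 50% (assumed), the chance of any value below 1% among 25 is about 0.2%; with a CV of 80% it is about 13%. This stands as far as it goes. It does not exclude BLQ troughs in children, because the pediatric predictions in Protocol 4.3 are redacted.

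Two further points stand. Upward bias arises only if zeros are dropped; read literally, the rule keeps them and gives 0. And the FAS table also shows the minimum, median and quartiles, so a BLQ value would be visible as a minimum of 0. The number of values behind the geometric mean would still be hidden, and the PK-subgroup table lists no median.

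A reader might infer that the plan will overstate the weekly trough, and most in children under 6. The documents do not support this. They give no readable trough for either cohort and no BLQ rate, and they do not say that zeros will be dropped.

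None of this supplies the missing rule for the geometric mean.

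**Conclusion.** The point holds as a defect in a stated rule. In both tables, any cell with a BLQ value has a geometric mean that is either 0 or computed without its lowest values, and the SAP does not choose. That conclusion rests on no assumption.

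The practical reach is small. It is most likely at Day 1 pre-dose. For on-treatment troughs the 7% to 29% range is conditional on the assumed LLOQ, on 1 or 2 BLQ values among 25, on the substitution value and on zeros being dropped; no single figure from it should be quoted as the size of the problem.

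A reader might also think that the trial's main trough result is compromised. It is not. The endpoint in SAP 4.4.4 counts participants whose average trough exceeds fixed thresholds and uses no geometric mean. The primary endpoint, inhibitor development, is untouched, and all analyses are descriptive (SAP 4.6). This is a minor correction worth making before database lock.

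**What to change.** Amend the BLQ sentence in both places in SAP 4.8.1 to say three things:

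1. Zero imputation applies to the arithmetic summaries only.
2. For the geometric mean, BLQ values take a stated positive value (for example LLOQ/2), or the geometric mean is shown as not calculated in any cell that contains BLQ values.
3. The number of BLQ values is reported in each cell.

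The cost is a short wording change and one extra table row; no new data are needed. The downside is that a substituted geometric mean depends on the value chosen. In the pre-dose example of step 4, LLOQ/2 gives 0.41 with an LLOQ of 0.5% and 0.68 with an LLOQ of 1%. Where most values in a cell are BLQ, showing it as not calculated, with the count, is the cleaner choice.

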4.8.2 Additional Immunogenicity analysis

4.8.2.1 Anti-drug antibody

Participant's ADA status (see definitions below) will be summarized on the safety analysis set. A participant with at least one anti-drug antibody (ADA) result available in the database is considered evaluable.

Participant's ADA status

- Pre-existing ADA: participant with at least one ADA positive prior to receiving BIVV001.
 - Treatment-boosted ADA: participant with pre-existing ADA positive and the ADA titer level anytime post-baseline is significantly higher than that at baseline. The post-baseline titer value that is at least 4-fold of pre-existing ADA titer value is considered significant.
 - Unclassified ADA: participant with pre-existing ADAs that cannot be classified as treatment-boosted ADA because of missing titer(s).
- Treatment-induced ADA: participant with all ADA negative (or missing) prior to receiving BIVV001 and at least one ADA positive at any time post-baseline.
- Treatment-emergent ADA: participant with treatment-induced or treatment boosted ADA.

ADA kinetics:

ADA response duration is defined as the date of last treatment-induced or treatment-boosted ADA sample minus date of first treatment-induced or treatment-boosted ADA sample +1. ADA response duration will be calculated only for participants with at least two treatment-induced or treatment-boosted ADA samples, irrespective of negative samples.

In case of participants with only one treatment-induced or treatment-boosted ADA, the ADA duration will be imputed to 0.

ADA response will be classified in the following categories for each participant:

- Persistent ADA response: an ADA response duration greater or equal than 16 weeks
- Transient ADA responses: an ADA response duration less than 16 weeks and the last sample in the study is not treatment-induced nor treatment-boosted.
- Indeterminate ADA response: ADA response that is neither persistent nor transient.

The number and percentage of participants with pre-existing ADA, treatment-boosted, unclassified, treatment-induced ADA, and treatment emergent ADA will be summarized by age cohort and overall for the Safety Analysis Set. The number and percentage of participants with different ADA kinetic status (ie, persistent, transient, indeterminate) will be summarized by age cohort and overall for the Safety Analysis Set. Median and 25th/75th quantiles, minimal and maximal of the ADA titer for pre-existing ADA, treatment-boosted, unclassified, treatment-induced ADA, and treatment emergent ADA will be provided.

A listing will be provided for confirmed positive anti-BIVV001 antibody information, including sample collection date and time, and ADA characterization testing. To evaluate the potential impact of ADAs and PK parameters, PK parameters for participants who have incidence of ADA positive (i.e., treatment-boosted or treatment-induced), along with the group mean of participants who are ADA negative at all times will be tabulated. As needed, FVIII activity level over time for participants who have incidence of ADA positive (ie, treatment-boosted or treatment-induced), along with the group mean of participants who are ADA negative at all times may be evaluated.

